The subjects who withdraw from the study will take appropriate treatment measures according to the judgment of the researchers.

Trial interventions

Enrolled patients will be randomized to undergo either taVNS or sham-taVNS. The taVNS treatment is performed at auricular cymba concha, while Sham-taVNS is performed at a sham point (elbow area). **Study Design and Protocol**

Enrolled patients are randomly divided into two groups (taVNS and sham-taVNS) with a ratio of 1:1 according to a computer-generated random digital table. The sample size is calculated by G*power analyses based on our preliminary study. One week before the start of the study, patients are asked to stop all constipation and IBS medications, including laxatives, prokinetic agents, probiotics, and antispasmodics. After one-week run-in period, patients in each group are requested to complete the following questionnaires once a week: the visual analog scale (VAS) for abdominal pain, IBS symptom severity score (IBS-SSS) for the overall IBS symptoms, IBS quality of life questionnaire (IBS-QOL) for patient's quality of life, Bristol Stool Form Scale (BSFS) for the stool type, Self-Rating Anxiety Scale (SAS) for anxiety, Self-Rating Depression Scale (SDS) for depression, and the bowel diary for the number of complete spontaneous bowel movements per week. Autonomic function is assessed at the baseline and after 4 weeks of treatment. by the spectral parameters of heart rate variability (HRV), calculated using spectral analysis of R-R intervals in electrocardiogram (ECG). A blood sample is taken at 8 a.m. at baseline and after 4 weeks treatment, Serum and plasma are separated and frozen at - 80 °C. The chronic taVNS and sham-taVNS intervention is performed twice a day (8am and 8pm) for half an hour each time, lasting for four weeks. During the run-in and treatment periods, only Macrogol 4000 and pinaverium are permitted for use, when the patient could not tolerate symptoms of constipation and abdominal pain. The flowchart is shown in Figure 1, and the study schedule is detailed in Table 1.

Figure 1. Flowchart of the study design.

	Baseline	Week 1	Week 2	Week 3	Week 4
Consent	×				
VAS	×	×	×	×	×
IBS-SSS, IBS-QOL	×	×	×	×	×
SAS, SDS, BSFS	×	×	×	×	×
HRV	×				×
Blood	×				×

Table 1. Study schedule. A bowel diary is recorded during the treatment.

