VAS, visual analog scale; IBS-SSS, IBS symptom severity score; IBS-QOL, IBS quality of life questionnaire; SAS, Self-rating Anxiety Scale; SDS, Self-rating Depression Scale; BSFS, Bristol stool form scale; HRV, heart rate variability.

Randomization

Enrolled patients are randomly divided into two groups (taVNS and sham-taVNS) with a ratio of 1:1 according to a computer-generated random digital table, which contains 21 odd numbers and 21 even numbers. Odd numbers represent taVNS, while even numbers represent sham-taVNS, and enter corresponding groups according to the sequence of patients.

Blinding

The patients are blinded to the type of treatment.

Serious adverse events (SAEs)

Pain at the stimulation site and allergy to the electrode are adverse events. Lowering the intensity of stimulation can relieve or eliminate pain. If the patient is allergic to the electrode, we will terminate the treatment and let the patient withdraw from the study.

Statistics

Quantitative variables are reported as means \pm standard deviations (SD), while categorical data qualitative variables are presented as absolute values and percentages. Categorical data are compared using the chi-squared test. The independent sample t-test is used to assess the difference between the sham-taVNS and taVNS groups; The paired student's t-test is applied to evaluate the differences before and after the taVNS or sham-taVNS treatment. *P*<0.05 is considered statistically significant.

Sample size estimation

G-Power software is used for calculation, and the steps are as follows:

- 1. T test, mean difference between two dependent means (two groups)
- 2. A priori: compute required sample size, given α , power, and effect size
- 3. Tails: One
- 4. Effect size: In the previous study, the number of spontaneous defecation was: 2.3 ± 2.1 (SD) in sham stimulation group; 3.7 ± 1.4 (SD) in true stimulation group. Therefore, the effect size dz=0.784.
- 5. $\alpha = 0.05$; $\beta = 0.2$, $1 \beta = 0.8$;

Based on the above data, G-Power software calculated total sample size: n = 42

Ethics committee review

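### Six outcomes are scored at Weeks 1 to 4, but the only between-arm test takes one unspecified value per patient; a baseline-adjusted repeated-measures model with one Week 4 contrast would be better.

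*Combined protocol and SAP*

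**What the plan says.** Under Study Design and Protocol, "patients in each group are requested to complete the following questionnaires once a week". Table 1 marks VAS, IBS-SSS, IBS-QOL, SAS, SDS and BSFS at baseline and at Weeks 1, 2, 3 and 4, which gives one baseline and four post-baseline scores per patient. The same section adds "the bowel diary for the number of complete spontaneous bowel movements per week". The diary has no row in Table 1; its caption says "A bowel diary is recorded during the treatment", so no baseline count is shown.

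The Statistics section lists a chi-squared test for categorical data and two tests for quantitative data. Between arms, "The independent sample t-test is used to assess the difference between the sham-taVNS and taVNS groups". Within each arm, "The paired student's t-test is applied to evaluate the differences before and after the taVNS or sham-taVNS" treatment. The threshold is P"<0.05 is considered statistically significant". The section names no week, change score, weekly average, repeated-measures model, baseline adjustment or rule for missing scores.

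HRV is outside this point: "Autonomic function is assessed at the baseline and after 4 weeks of treatment". Blood is taken at the same two times. Each has only one post-baseline value.

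**The concern.** An independent t-test needs one number per patient. With four post-baseline scores, someone must choose that number, and the plan leaves the choice open. Two natural choices each have a cost.

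- **Week 4 only.** A patient who leaves after Week 2 has two post-baseline scores on file and contributes none of them. The protocol lists seven withdrawal criteria and also withdraws patients who are allergic to the electrode. The sample size makes no allowance for losses; withdrawals are only counted at the end.
- **Each week in turn.** All the scores are used, but every outcome gets four tests at 0.05, with no correction and no statement of which one counts.

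The paired test does not help. It forms one before-after difference within an arm and makes no comparison between arms. With 21 patients per arm, both the data of those who leave and the baseline scores are worth using.

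**Working it through.** **Inputs from the documents.** Sample size estimation gives 2.3 (SD 2.1) for sham and 3.7 (SD 1.4) for active stimulation, one-tailed alpha 0.05, power 0.80 and total 42. Randomization gives 21 per arm.

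**Assumptions, since the documents give no figure.** Equal SD each week; equal correlation rho between weeks, 0.5 to 0.8 unless stated; 3 patients per arm lost after Week 2. The planned effect size comes from counts of spontaneous defecation in a previous study. Using it for the questionnaires is illustrative.

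**1. The plan's own figure.** Pooled SD = sqrt((2.1² + 1.4²)/2) = 1.785, so d = 1.4/1.785 = 0.784. An independent t-test with 21 per arm (noncentral t, 40 df) has one-sided power 0.803, so 42 reproduces. Two-sided power is 0.699. The calculation uses one value per patient and assumes no repeated-measures gain.

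**2. Week 4 only, with losses.** At 18 completers per arm, one-sided power falls from 0.803 to 0.746.

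In a mixed model with arm-by-week terms, the Week 1 and 2 scores of the 3 who left help to estimate the Week 4 mean. The share of Week 4 variance explained by Weeks 1 and 2 is R² = 2·rho²/(1 + rho). The effective number per arm is 1/[(1 − R²)/18 + R²/21].

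| rho | R² | Calculation | Effective n per arm |
|---|---|---|---|
| 0.5 | 0.333 | 1/(0.0370 + 0.0159) | 18.9 |
| 0.8 | 0.711 | 1/(0.0160 + 0.0339) | 20.0 |

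The model therefore recovers 0.9 to 2.0 of the 3 patients lost per arm, before any baseline adjustment.

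**3. Week 4 only, complete data.** Without baseline, the Week 4 contrast from an unstructured model with arm-by-week terms equals the difference in Week 4 means, so the gain is zero. Baseline adjustment multiplies the variance by 1 − rho², if baseline correlates with Week 4 at rho:

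- rho 0.5: 1 − 0.25 = 0.75
- rho 0.8: 1 − 0.64 = 0.36

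**4. Each week tested.** With four independent tests, the chance of at least one false positive per outcome is 1 − 0.95⁴ = 18.5%. By simulation (21 per arm, two-sided 0.05) it is 17.5% at rho 0.3, 15.8% at 0.5, 13.2% at 0.7 and 9.5% at 0.9.

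**5. Would a Week 3-4 mean be better?** Its variance factor is (1 + rho)/2, or 0.75 to 0.90.

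- If the effect is the same in both weeks, one-sided power is 0.893 to 0.839, against 0.803 for Week 4 alone.
- If the effect builds up as 25, 50, 75 and 100% of its Week 4 size, the mean effect is (0.75 + 1)/2 = 0.875 of it, and power is 0.810 to 0.745. Break-even is at 0.875² = (1 + rho)/2, so rho = 0.53. Above that, the mean loses to Week 4.

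**The case against.** A reader might infer that three of the four scores are discarded and that precision is certainly lost. The documents do not support that. They never say which value enters the t-test: it could be Week 4, each week or a patient's weekly mean. A t-test on a weekly mean is still the planned test, and it would use several weeks. What the documents do show is that the value is unspecified and that no stated method combines the weeks. It would also be loose to say that both planned tests take one number per patient, because the paired test uses a before and an after score.

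A reader might also infer that pooling weeks always raises power. It does not. With complete data the model leaves an unadjusted Week 4 comparison unchanged, and averaging Weeks 3 and 4 changes the target and can lose power. No section says that the effect is constant over the weeks.

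Two further objections stand in part. An unadjusted t-test at one week is valid in a randomised trial, so with complete data this is a matter of efficiency and specification, not of bias. And the dropout figure is assumed: if nobody withdraws, the gain in step 2 disappears. Neither objection removes the value of naming one contrast, or of using a baseline score that is already collected for all six questionnaires.

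**Conclusion.** The point holds in a limited form. For the six weekly questionnaires, and for the diary without a baseline term, the stated between-arm method is under-specified, and a better one is available from data already planned. The gain has three parts:

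- partial data are kept after withdrawal, which is modest in size and rests on the assumed losses and rho;
- baseline adjustment, which may be the larger gain but depends on how well baseline predicts Week 4;
- one prespecified test per outcome instead of up to four, which removes the 9.5% to 17.5% exposure within each outcome but does not address multiplicity across outcomes.

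The change is advisable. It is not needed for the validity of a single prespecified Week 4 test with complete data.

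**What to change.** For each of VAS, IBS-SSS, IBS-QOL, SAS, SDS and BSFS, replace the between-arm t-test with one mixed model for repeated measures of Weeks 1 to 4. Include arm, week, arm-by-week, baseline score and baseline-by-week, with an unstructured covariance. Prespecify one between-arm contrast, at Week 4, and state its sidedness. For the weekly diary count, use the same model without the baseline terms, unless a run-in count is recorded. The mean of Weeks 3 and 4 may be a supporting contrast, labelled as such. The paired tests can stay as within-arm description. HRV and blood need no change on this account.

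The cost is a revised Statistics paragraph and a little more programming, with no new visits, data or patients. The model assumes that missing scores are missing at random given the scores observed, and the plan should say so. The timeline puts data analysis in August to October 2020, while the document is dated 25 May 2022. If outcome data had been seen before the change, the model should be reported as a later choice and not as prespecified.

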	treatment. $P < 0.05$ is considered statistically significant.				

Clinical study summary

Background

Irritable bowel syndrome (IBS) is a clinical syndrome characterized by persistent or intermittent attacks, abdominal pain, abdominal distension, defecation habits and (or) changes in stool characteristics. According to the world-wide population survey, the global prevalence of IBS is about 11.2% (95% CI: 9.8-12.8) (1), and the prevalence of IBS in China is about 5-10% (2). According to Rome IV diagnostic criteria (3), IBS can be divided into four types: constipation type (IBS-C), diarrhea type (IBS-D), mixed type (IBS-M) and unclassified type (IBS-U). Among them, IBS-C accounted for about 27% of the total prevalence (4). The persistent or intermittent symptoms of patients bring a lot of inconvenience and pain, resulting in a significant decline in the quality of life, but also increased the burden of the social health system.

The etiology and pathogenesis of IBS have not been fully elucidated, but many factors are involved, including genetic factors, intestinal infection, mucosal immune and inflammatory response, altered gastrointestinal motility, visceral hypersensitivity, post infectious reactivity, brain-gut interactions, disturbance of intestinal flora, food sensitivity or stress(5-8), among which altered gastrointestinal motility and visceral hypersensitivity have been considered to be the main pathophysiological basis. At present, various drugs are used for pharmacologic treatment. Laxatives and prokinetics are used for constipation, while antispasmodics and antidepressants are prescribed for abdominal pain, which in turn may impair gastrointestinal motility and thus could worsen constipation (9, 10). Additionally, such medications can only relieve symptoms temporarily, and long-term medication is expensive and easy to relapse after withdrawal (11). Accordingly, patients often seek complementary and alternative therapies (12).

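### The sample-size section names a paired test for a two-group trial: as labelled it gives 12, while the stated 42 needs independent means and one tail, and the Statistics section states no sidedness

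*Combined protocol and SAP*

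**What the plan says.** The Sample size estimation section lists its G*Power inputs as follows.

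- Test: "T test, mean difference between two dependent means (two groups".
- Sidedness: one tail.
- Earlier data on the number of spontaneous defecations: "2.3 ± 2.1 (SD) in sham stimulation group" and 3.7 with SD 1.4 under true stimulation.
- Effect size: "Therefore, the effect size dz=0.784".
- Alpha 0.05 and power 0.80.
- Result: "Based on the above data, G-Power software calculated total sample size: n = 42".

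The rest of the plan describes a parallel-group trial. Under Randomization, allocation is 1:1 from a table "which contains 21 odd numbers and 21 even numbers". Under Statistics, "The independent sample t-test is used to assess the difference between the sham-taVNS and taVNS groups", and the paired t-test is kept for before/after change within a group. The Statistics section and the Statistical analysis row of the synopsis both set the threshold at P<0.05 and do not say whether it is one- or two-sided.

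**The concern.** Dependent means and dz belong to a paired design, in which each patient supplies both measurements. This trial has none of that in its between-group comparison, so the stated method does not match the comparison it is meant to size. A reader who enters the listed settings into the software does not get 42.

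Correcting the label leaves a second gap. The one tail appears only among the sample-size inputs, while the text that defines significance is silent. Two things depend on it: whether the stated 80% power is true of the planned analysis, and where the line between a significant and a non-significant result falls. If the analysis text does not fix that line, it can be settled after the data are seen.

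**Working it through.** **Inputs** (all from Sample size estimation, Randomization and Statistics): means 2.3 and 3.7, SDs 2.1 and 1.4, alpha 0.05, power 0.80, one tail, 21 per arm, independent-samples t-test. Power is computed from the exact noncentral t distribution, which is the method G*Power uses.

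**1. What 0.784 is.** The difference is 3.7 − 2.3 = 1.4. The pooled SD with equal group sizes is sqrt((2.1² + 1.4²)/2) = sqrt(6.37/2) = 1.785. Then d = 1.4/1.785 = 0.784, the independent-groups Cohen's d. A dz would be 1.4/sqrt(6.37 − 5.88r), where 5.88 = 2 × 2.1 × 1.4 and r is the within-pair correlation. The plan gives no r. With r assumed, dz is 0.555 at r = 0, 0.756 at r = 0.5 and 1.0 at r = 0.75.

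**2. Reproducing the plan's 42.** For independent means the noncentrality is d × sqrt(n/2), with 2n − 2 df. For a paired test it is dz × sqrt(n), with n − 1 df. At 0.784:

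| Test | Sides | One step below | First n reaching 80% | Total |
|---|---|---|---|---|
| Paired (as labelled) | one | 11: 78.0% | 12: 81.6% | 12 |
| Paired | two | 14: 77.4% | 15: 80.6% | 15 |
| Independent | one | 20 per arm: 78.5% | 21 per arm: 80.3% | **42** |
| Independent | two | 26 per arm: 79.2% | 27 per arm: 80.7% | 54 |

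Among these, only independent means with one tail returns 42.

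**3. Could a paired calculation from the same data give 42?** A one-tailed paired n of 42 needs dz between 0.390 and 0.395. The smallest dz these SDs allow, at r = −1, is 1.4/sqrt(6.37 + 5.88) = 1.4/3.5 = 0.40. So no choice of r makes a one-tailed paired calculation return 42.

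**4. Power at 42 by sidedness.** With 21 per arm and d = 0.784, power is 80.3% one-sided and 69.8% two-sided. Allowing for the unequal SDs (200,000 simulated trials, normal data, SDs 2.1 and 1.4) gives 80.2% and 69.9%, so the pooled SD is not driving the result. The d detectable with 80% power is 0.781 one-sided and 0.886 two-sided. The latter is 0.886 × 1.785 = 1.58 defecations, against the 1.4 assumed.

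**5. Where the conclusion changes.** On 40 df the critical t is 1.684 one-sided and 2.021 two-sided. Multiplying by 1.785 × sqrt(2/21) gives observed differences of 0.93 and 1.11. If the assumed effect is true, the result falls between these limits with probability of about 80.3% − 69.8% = 10.5%.

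**The case against.** The best defence is that nothing in the conduct of the trial depends on the wrong label. The same line adds that there are two groups, the randomization table fixes 21 and 21, the Statistics section names the right test, and nobody would enrol 12. One tail and alpha 0.05 are stated openly, P<0.05 is compatible with them, and the documents' only statement on sidedness supports 80%. On this view a clarifying sentence is enough.

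Much of this is fair. The label alone does not make 42 wrong, and the 70% figure is conditional on a two-sided reading that the plan never states. But the stated steps still do not give the stated number. The threshold in the Statistics section also governs every other comparison, including the chi-squared tests, so a one-tail setting in a wrongly named calculation does not settle how it is read.

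Three further cautions stand.

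- The 80.3% requires all 42 patients to be analysed: 21 and 20 gives 79.4%, and 20 per arm gives 78.5%. No dropout allowance is stated.
- The outcome sized is spontaneous defecations, with no time unit, whereas the bowel diary counts complete spontaneous bowel movements per week. The power figures apply to the former.
- The document is dated May 2022, while its timeline puts data analysis in August to October 2020. If that timeline was kept, a sidedness chosen now would be post hoc and should be reported as such.

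None of these removes the error.

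**Conclusion.** The concern holds. The test name and the dz label are wrong for this design. The effect size and the total of 42 are right for two independent means, one-tailed. As labelled, the calculation gives 12.

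The part with consequences is sidedness. If the between-group test is one-sided, the stated power holds (80.3%) and the result is judged at one-sided 5%. If it is two-sided, power at 42 is 69.8%, about 10 percentage points below the plan's figure. These figures assume the earlier study's means and SDs, approximately normal data, all 42 patients analysed, and the number of spontaneous defecations as the outcome. They say nothing about power for abdominal pain or the other scales.

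**What to change.** In Sample size estimation, replace the test name and effect-size label with: difference between two independent means, Cohen's d = 0.784, allocation 1:1, for the number of spontaneous defecations. Then state one sidedness, the same in Statistics, in the synopsis and in Sample size estimation.

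- **If two-sided:** change the one-tail entry, keep 42, and restate power as about 70% for d = 0.784 (80% for d = 0.89).
- **If one-sided:** keep 42 and the 80% power, with the note that it assumes all 42 are analysed, and add to Statistics that this comparison is judged at one-sided 0.05.

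The change is to wording only and adds no patients or visits. The cost falls on the sponsor: either the stated power drops to about 70%, or the report must say openly that the comparison was judged at one-sided 5%.
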